arterial line is not available the non-invasive cuff will be cycled every 5 minutes. Continuous vital signs will be extracted from the Sickbay software application, which collects physiologic data on all NCCU (see IRB00132987 Multimodality Neuromonitoring in the Neurocritical Care Unit). A clinician will observe the patient at all times during the session for signs of pain and discomfort and will administer the behavioral or visual analog pain scale every 5 minutes during the session depending on the patient's level of consciousness. Patient tolerance will be defined as the absence of the following: decline in neurological examination; sustained change in intracranial pressure, blood pressure, heart rate or oxygen saturation outside of prescribed goals per established patient specific plan of care; an increase in pain as measured by the behavioral pain scale or numeric pain rating scale not easily ameliorated by position change by the clinician; and accidental tube/device/catheter removal.^{22,34} Manual muscle strength testing using the Medical Research Council Sum Score will be performed by a clinician before the first session on days three and seven for patients in the control group. General strength will be assessed using a hand-held dynamometer for patients able to follow simple commands before the first session on days three and seven for patients in the control group. Other relevant covariates will be extracted from the medical record such as delirium screening, hospital acquired infections, volume of hematoma and cerebral edema on routine CT scans and body temperature.

The second control group, retrospective observational cohort, will consist of ischemic and hemorrhagic stroke patients admitted to the NCCU on the Johns Hopkins Hospital and Johns Hopkins Bayview campuses from March 16, 2020 through the end of the prohibition of tier II and III studies declared by the Johns Hopkins University Institutional Review Board. All data collection will be accomplished through retrospective chart abstraction. Face-to-face contact will not be required. The same clinical variables will be collected for this cohort to the extent that they are recorded in the medical record from admission to 90 days after the initial ischemic or hemorrhagic stroke.

The following samples will be obtained for the intervention + usual care group and the control group, usual care only:

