Usual care in the NCCU consists of evaluation and treatment by physical and occupational therapists assigned to the neurosciences service when an order for evaluation and treatment is entered by medical providers. Patients may be seen up to 5 times per week depending on their level of participation and intensity of therapy required, however many patients with sICH particularly those in coma are treated by therapists 2 times per week. Nursing staff in the NCCU provide passive range of motion and progressive a patient's mobility from supine to upright positioning, sitting at the side of bed, transferring to chair, lift assisted transfer to chair and ambulation as the patient's condition allows. All usual care activities will be recorded by the study team via extraction from the medical record. Usual care during the pandemic is similar to the care described above however, due to resource constraints it is possible that care focused on mobility and recovery was reprioritized in order to provide acute and intensive care for other patients.

Table 1. Study Activities Schedule for the intervention and prospective control group

	Admission day 1-2	Study day 1 = hospital day 3	Study day 2 = hospital day 4	Study day 3 = hospital day 5	Study day 4 = hospital day 6	Study day 5 = hospital day 7	Study day 6 = hospital day 8	Study day 7 = hospital day 9	Day of ICU transfer	30 days after hemorrhage (-10, +30 days)
Screening, Inclusion/Exclusion, Consent	X									
Intervention and monitoring										
Cycle ergometry 20 minute sessions (twice each study day)		XX								
Vital signs (BP, HR, RR, SpO ² , ICP)		X	X	X	X	X	X	X		
Pain scores		X	X	X	X	X	X	X		
Physiologic outcomes for the intervention and control groups										
Blood draw (IL1- β , IL-6, TNF- α , IL-10, CRP, BDNF)		X		X				X		
Saliva sample for cortisol		X		X				X		
CSF sampling, if a external ventricular		X		X				X		

drain is in place										
Outcome measures										
Medical Research Council Sum Score (strength testing) ²¹		X		X				X	X	X
Grip strength		X		X				X	X	X
Modified Rankin scale score	X								X	X
Barthel Index ¹²									X	X
Sunnybrook Neglect Assessment Procedure (SNAP) ³¹		X							X This battery will only be completed if the patient was found to have neglect on the initial assessment.	X This battery will only be completed if the patient was found to have neglect on the initial assessment.
Questionnaires										

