a. Primary outcome variable.

Pro-inflammatory cytokines: IL-1 β , TNF α , IL-6; Anti-inflammatory/repair factors: IL-10, BDNF

b. Secondary outcome variables will be measured at discharge and 30 days post-intracerebral hemorrhage or acute ischemic stroke.

- Modified Rankin Scale (mRS)
- Barthel Index will be measured at discharge and 30 days
- Medical Research Council Sum Score and dynamometry to measure muscle strength
- Discharge location (e.g., home, nursing facility), although not well studied, is commonly associated with physical function at discharge.
- SF-12
- Vital signs (e.g., heart, rate, blood pressure, respiratory rate)
- Delirium positive days
- Hospital acquired infections (e.g., catheter associated urinary tract infection and central line associated blood stream infection)
- CSF cytokines and repair factors
- Stroke Impact Survey

c. Statistical plan including sample size justification and interim data analysis.

Sample size was calculated for a fully powered trial and 9% of this sample size will be used for this pilot according to Cocks' methodology.¹⁰ An effect size of 0.28 was used, based on a published single group observational study in critically ill patients with a primary outcome of cytokine change.⁴⁷ Detection of an effect size of 0.28 with power of 80% and an α of 0.05 requires a sample size of 400 for a full trial and 9% represents a pilot sample size of 36 participants. Due to the enrollment of two stroke phenotypes, ischemic and hemorrhagic, we will analyze each cohort separately, therefore 40 participants per cohort are required. Accounting for attrition, up to 100 participants may be consented in order to enroll up to 40 participants per cohort. Each cohort will have 20 participants in each of two arms, intervention and control. It is estimated that at least 3-5 patients will be enrolled per month over 18 months.

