Descriptive statistics will be used to report sociodemographic variables. Baseline characteristics will be compared between the two groups. If they are found to be similar, post-intervention outcomes will be compared between the groups. If the baseline characteristics are found to be different, an adjusted analysis as described below will be conducted. Mean (SD) or median (IQR) will be used to describe continuous variables, and frequency (%) will be used for categorical variables. Mean differences in cytokines between the three time points (baseline, day 3 and day 7) will be calculated for each participant in the intervention and control groups. We will also plot data over time by group. Assumptions of normality will be checked and appropriate parametric or non-parametric tests will be used to detect absolute mean differences due to the small sample size, with an a priori significance level of 0.05, although the primary aim of this study is to estimate effect size. Data quality will be ensured by analyzing all samples in duplicate and procurement of samples will be performed by the same investigator. Statistical analysis will be performed using Stata 14.0 (College Station, Texas).

Primary aim (1): To determine whether a regimen of twice daily 20-minute sessions of CE plus usual care administered to patients with sICH and AIS (n=20) increases cytokines of the M2 phenotype and decreases cytokines of the M1 phenotype within 10 days of sICH when compared to a similar group of patients with sICH receiving usual care only (n=20).

The effect size, absolute difference between the two groups and the standard error of the difference will be estimated. The standardized difference will be estimated using Cohen's d. A two-sample t-test will be used to detect differences between post-test outcomes. If the baseline outcome is different, an analysis of covariance (ANCOVA) will be used to compare the outcomes between the two groups adjusting for the baseline difference as a covariate.

Hypothesis: Patients in the CE group will demonstrate an increase in cytokines of the M2 phenotype and a decrease in the M1 phenotype when compared to the group receiving usual care only.

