Aim 2: To determine the effects of twice-daily, lower extremity CE of 20 minutes duration plus usual care compared to usual care alone and a third retrospective cohort of patients receiving usual care during the COVID-19 pandemic on, the immediate and sustained physical impairment and disability scores at NCCU discharge and 30 days after hemorrhage.

Data from this aim will be analyzed in the same fashion as described above.

Hypothesis: The CE group will demonstrate decreases in 90-day modified Rankin Scale score, increases in the Medical Research Council sum score (muscle strength) and grip strength, less delirium positive days and hospital acquired infections.

d. Early stopping rules.

If a patient meets the following stopping criteria on >2 consecutive sessions the patient will be withdrawn from the study: change in neurological examination, sustained change in intracranial pressure, blood pressure, heart rate, or oxygen saturation that is outside of provider-prescribed range or significant pain exacerbated by mobilization.

6. Risks

a. Medical risks, listing all procedures, their major and minor risks and expected frequency.

The risks of this study are designed to be minimal. Potential risks to the participant include the following: hemodynamic instability, increased intracranial pressure, skin breakdown associated with the supine cycle ergometer, pain, muscle spasm and musculoskeletal injury.

b. Steps taken to minimize the risks.

Patients are continuously monitored on a cardiorespiratory monitor with oxygen saturation, heart rate, intracranial pressure (when applicable) and blood pressure, measured by arterial catheter or non-invasive cuff. Blood pressure, heart rate, oxygen saturation, respiratory rate and intracranial pressure will be measured and recorded continuously using the Medical Informatics, Sickbay software application currently installed in the NCCU and collecting data from all cardiorespiratory monitors. Pain will be measured and documented every 5 minutes visual analog scale or behavioral pain scale in patients unable to report pain level.

The NCCU is staffed 24 hours per day by a dedicated team of Neuro Intensivists, fellows and resident physicians assigned exclusively to the unit who can respond immediately to physiologic changes or adverse events when notified. A chain of command is followed when a primary provider is not available to respond due to other emergent patient care duties.

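### Aim 2 counts delirium-positive days and hospital-acquired infections with no common window and no rule for death, coma, unscreened days or discharge, so lost days can read as benefit

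*Combined protocol and SAP*

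**What the plan says.** Study Statistics, b (secondary outcomes) lists "Delirium positive days" and, as a separate item with two examples, hospital-acquired infections. The Aim 2 hypothesis in Study Statistics, c expects "less delirium positive days and hospital acquired infections" with cycling, so fewer is the direction of benefit.

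The data come from charts. Section 3a states: "Other relevant covariates will be extracted from the medical record such as delirium screening, hospital acquired infections".

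On analysis, Aim 2 says only: "Data from this aim will be analyzed in the same fashion as described above". That refers back to Aim 1: "A two-sample t-test will be used to detect differences between post-test outcomes". ANCOVA is used if baseline differs, non-parametric tests are allowed, and testing is done "with an a priori significance level of 0.05".

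Time frames differ between places:

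- Section 3a (study design) has randomised patients enrolled on day 3 of illness and followed for seven consecutive days.
- Study Statistics, b ties the secondary outcomes to discharge and 30 days.
- Section 3a (second control group) abstracts the pandemic cohort's charts from admission to 90 days after the stroke.

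No section says over which days delirium or infection is counted, what the denominator is, or how days lost to death, coma, missed screening or discharge are treated. Section 4 notes that the modified Rankin scale includes death, but nothing links death to these two outcomes.

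**The concern.** A delirium-positive day can be recorded only if the patient is alive, in hospital, screened and responsive enough to assess. A patient who dies early, stays comatose or leaves early has few such days, and the hypothesis reads a low count as success. For infections, death and a short stay act the same way by shortening time at risk.

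A difference between groups in survival, consciousness or stay could therefore appear as an effect on delirium or infection when there is none, in either direction. A treatment that kept more patients alive and awake could look worse on delirium. Study Statistics, c says the pilot's main purpose is to estimate effect size, so a distorted estimate could be carried into a larger trial.

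**Working it through.** **The plan's own figure.** The protocol gives no number for delirium or infection. Its only benchmark is the sizing effect of 0.28 (80% power, α 0.05, taken as two-sided). Per arm: 2 × (1.960 + 0.842)² / 0.28² = 2 × 7.849 / 0.0784 = 200.2, so 201 per arm and 402 in total, against the stated 400; 9% × 400 = 36. These figures reproduce and this point does not affect them. I use 0.28 only as a yardstick.

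**Step 1: simple illustration (all rates assumed).** Assessable patients average m = 3 delirium days in both arms, and a share p who die or stay comatose contribute 0. Mean = m(1 − p).

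- p = 20% control, 10% cycling: 3 × 0.80 = 2.40 v 3 × 0.90 = 2.70. Cycling looks 0.30 days worse.
- p = 30% v 15%: 3 × 0.70 = 2.10 v 3 × 0.85 = 2.55. The gap is 0.45 days.

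Cycling halves death or coma and leaves delirium unchanged, yet it scores worse. To scale this, take an SD s of 1.5 to 2.5 days among assessable patients (assumed), with variance = (1 − p)s² + p(1 − p)m². The pooled SD is 1.74 to 2.54 in the first case and 1.81 to 2.52 in the second. Then d = 0.30/2.54 = 0.12 up to 0.45/1.81 = 0.25. With 20 per arm the standard error is SD × √(2/20), about 0.55 to 0.80 days, so each gap is below one standard error.

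**Step 2: simulation.** 20,000 trials, 20 per arm, two-sample t-test on delirium days. Daily risks were equal in both arms: delirium averaging 0.4 per assessable day (varying between patients) and infection 0.02 per day. Otherwise death was 1% per day, 25% were comatose (assessable on 20% of days) and mean stay was 12 days. All rates are assumed. The last column is the share of trials significant in the misleading direction (nominal 2.5%).

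| What differs (control → cycling) | Window | Delirium days | d | Misleading |
|---|---|---|---|---|
| Death 1% → 3% per day | 7 days | 2.02 → 1.92 | −0.05 | 3.5% |
| Stay 12 → 8 days | 7 days | 2.03 → 1.81 | −0.11 | 5.1% |
| Stay 12 → 6 days | 7 days | 2.02 → 1.58 | −0.22 | 9.6% |
| Coma 40% → 15% | 7 days | 1.71 → 2.23 | +0.25 | 11.9% |
| Death 1% → 3% per day | 28 days | 3.55 → 3.12 | −0.11 | 4.9% |
| Coma 40% → 15% | 28 days | 3.03 → 3.90 | +0.21 | 10.0% |
| Stay 12 → 8 days | 28 days | 3.57 → 2.44 | −0.31 | 13.5% |
| Stay 12 → 6 days | 28 days | 3.55 → 1.85 | −0.49 | 30.8% |

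With nothing differing, total rejection was 4.9% (7 days) and 4.7% (28 days). Infection with stay 12 → 8 days fell from 11.9% to 10.7% (7 days) or from 19.5% to 14.0% (28 days). Changing coma left infection unchanged. Per assessable day, delirium was about 0.40 in both arms in every row. A short window shrinks the death and stay artefacts but not the coma artefact.

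**Step 3: pandemic cohort.** Take a 12-day stay and equal daily risks in both groups. Counting hospital days 3-9 gives 7 days at risk; counting from admission gives 12.

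- Delirium days (risk × days): 1.4 v 2.4, 2.8 v 4.8 and 4.2 v 7.2 at assumed daily risks of 0.2, 0.4 and 0.6.
- Infection, 1 − (1 − risk)^days: 6.8% v 11.4%, 13.2% v 21.5% and 19.2% v 30.6% at assumed daily risks of 1%, 2% and 3%.

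The gap comes from the window alone.

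**Step 4: Step 1 rescored.** Over 7 days, score assessable patients 7 − 3 = 4 days alive and free of delirium and coma, and the others 0. Means become 4 × 0.80 = 3.2 v 4 × 0.90 = 3.6, and 4 × 0.70 = 2.8 v 4 × 0.85 = 3.4. The difference now points the right way.

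**The case against.** These are secondary outcomes in a pilot whose primary outcome is cytokines. The Objectives section calls delirium and infections covariates, and the Aim 2 statement in Study Statistics, c names only impairment and disability scores. Randomisation protects the main comparison: if cycling changes none of death, coma or stay, type I error stays near 5%. If cycling does shorten stay, fewer in-hospital delirium days is partly a real consequence, and whether to count it is a choice of estimand. A large mortality difference would show in the Rankin scale. Section 4 excludes patients with a Glasgow Coma Score of 3 at 48 hours and those for whom withdrawal of life support is under consideration.

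Most of this stands, and it limits the weight of the point. It does not supply the missing window or rules, and the hypothesis still reads fewer as better.

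Several stronger readings are tempting but unsupported:

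- **Coma is common in this population.** The usual-care text says "many patients with sICH particularly those in coma are treated by therapists 2 times per week". That describes therapy frequency and gives no prevalence; it shows only that some patients in coma are expected.
- **Coma lowers infection counts.** Nothing in the documents supports this. For infections the route is death and length of stay.
- **Infections are specified as raw counts.** The plan does not say count, rate or yes/no, and it summarises categorical variables as frequencies.
- **Pandemic patients stayed longer.** The documents mention changed visits and reprioritised mobility care, not length of stay. What differs on paper is the abstraction window.

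**Conclusion.** The point holds in limited form. Fewer delirium-positive days and infections are read as benefit with no common window and no handling of death, coma (delirium only), unscreened days or discharge.

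Between the randomised arms this misleads only if death, coma or stay differs, through treatment or chance. In a 7-day window the effect is modest: every simulated shift was below d = 0.28. Larger values (−0.31, −0.49) need a 28-day window and stays of 12 v 8 or 6 days.

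Against the pandemic cohort the time at risk may differ by design, and randomisation gives no protection. It is may rather than does, because the seven-day statement is general and the secondary outcomes are also tied to discharge.

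The true size cannot be computed from the documents, which give no rates for delirium, infection, death, coma or stay. The 0.30 and 0.45-day gaps are illustrations, not estimates of bias. The primary cytokine analysis and the sample size are unaffected. This is an inexpensive improvement that should be made.

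**What to change.** 1. Count both outcomes over one fixed window, study days 1-7 (hospital days 3-9), in all three groups.
2. Replace delirium-positive days with days alive and free of delirium and coma in that window. Score a patient who dies within it as 0, and compare groups by a rank-based or proportional-odds method.
3. State in advance how days after live discharge are scored. Counting them as free still rewards early discharge, so add a sensitivity analysis, for example delirium days per assessable day.
4. Tabulate deaths, coma days, delirium days, unscreened days and days after discharge by group.
5. Report infections over the same window as the proportion infected and per 100 patient-days. Show deaths alongside, because a rate per patient-day still ignores death as a competing event.
6. Treat the pandemic-cohort comparison as descriptive; redefining the outcome does not make that group comparable.

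No new patient assessments are needed. Daily level of consciousness must be abstracted where charted. Section 3a does not name it among the abstracted variables, and for the pandemic cohort it exists only as recorded. The composite mixes death and coma with delirium, which is why its components must be tabulated.
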